9. TIMELINE

The total study period is estimated at 43 months, from January 1st 2017 to July 31st, 2020. This includes approximately 4 months of preparatory time 30 months of active enrolment (starting on May 1st, 2017), six months of follow-up after last enrolment, and 3 months for data cleaning, analysis and dissemination.

10. DATA ANALYSIS

An outline of the analysis plan for the primary objectives is presented here.

Primary analyses will be intent-to-treat (ITT) based on randomization allocation to the 3-day course of azithromycin or placebo. For each analysis, azithromycin will be compared to those treated with placebo.

The primary end-points in this trial are proportion of deaths in the 180 days post-enrolment and change in length-for-age z-score in the 90 days post-enrolment by study arm

Deaths will be ascertained by study staff either through family reports, community health workers, hospital staff, or determined at follow-up visits. Date will be determined by verbal autopsy or medical records in cases of facility deaths.

Length will be assessed using a length board at enrolment and at the day 90 follow-up visit by study staff trained in anthropometry. Length will be measured twice at each visit, a third time if the two repeated measures varied by more than 10%, and the median length used for analysis. Length-for-age z-scores will be calculated using the WHO ANTHRO software. Implausible length values will be considered on a case-by-case basis within each site and implausible lengths set to missing.

Loss to follow-up will be determined at 180 days after enrolment and defined as non-attendance at the 180-day follow-up visit and inability to be contacted after three subsequent attempts. All analyses will utilize a complete case analysis other than in time-to-event analyses where children who are lost to follow-up will be censored at the date of last contact with the study team. All hypothesis testing will utilize an alpha of 0.05 to determine statistical significance.

10.1 Primary Objectives

1. *To compare rates of all-cause mortality in the 180 days following enrolment for an episode of high risk diarrhoea without dysentery among children 2 to 23 months of age living in low resource settings who are randomized to receive a 3-day course of azithromycin or placebo.*

Period prevalence of death will be compared between randomly-assigned treatment groups using relative risk regression. Mortality will be defined as a binary variable and will be defined as any event of death from time of randomization to end of day 180. Time to death will not be considered. Censored individuals will be retained in the denominator. For the primary ITT analysis, the following model will be used:

$$E(Y|\text{randomisation arm}) = e^{(\beta_0 + \beta_1 X_{azm})}$$

where x_{azm} is an indicator variable specifying randomized to the azithromycin group ($x_{azm}=1$) or not ($x_{azm}=0$). The risk ratio comparing the risk of death in children randomized to azithromycin vs. placebo will be determined by e^β . The statistical significance of this comparison will be determined by Wald test.

If the baseline assessment of randomization reveals an imbalance in characteristics between the randomization arms, we will evaluate these characteristics as potential confounders in a sub-analysis secondary to the ITT. The following baseline characteristics will be evaluated for balance between randomization arms (median age, stunting prevalence, wasting prevalence, prevalence of “some” and “severe” dehydration, site [Bangladesh, India, Kenya, Malawi, Mali, Pakistan, Tanzania], hospital admission, and median duration of diarrhoea). Potential baseline confounders will be added stepwise in the relative risk model with randomization arm as follows:

$$e^{(\beta_0 + \beta_1 X_{azm} + \beta_i X_i)}$$

Where i are the baseline characteristic(s) included in the model. These will be maintained in the model if their inclusion in the model changes the hazard ratio by more than 10%. Also, in a sub-

analysis, separate analysis for each site (Bangladesh, India Kenya, Malawi, Mali, Pakistan, Tanzania) will be presented to describe differences in treatment effects between sites (no formal hypothesis tests within each site stratum will be performed).

In a per-protocol analysis, also secondary to the ITT analysis, relative risk regression will be fit as described above among the subset of children with documented completion of the full course of treatment (direct observation of 3 daily doses and) with at-risk-time beginning on date of observed third dose.

2. *To compare changes in linear growth (Δ LAZ) in the 90 days following enrolment for an episode of high risk diarrhoea without dysentery among children 2 to 23 months of age living in low resource settings who are randomized to receive a 3-day course of azithromycin or placebo.*

Analysis strategy: Linear regression model will be used to compare mean Δ LAZ across the treatment groups in surviving children. Δ LAZ will be operationalized as the difference in LAZ between the 90-day follow-up visit and LAZ at baseline. For the primary ITT analysis, the following model will be used:

$$E(Y|\text{randomisation arm}) = \beta_0 + \beta X_{azm}$$

where Y =mean Δ LAZ, and x_{azm} is an indicator variable of being randomized to the azithromycin group ($x_{azm}=1$) or not ($x_{azm}=0$). The mean difference in Δ LAZ in children randomized to azithromycin vs. placebo will be determined by (β). The statistical significance of this comparison will be determined by independent t-test.

If the baseline assessment of randomization reveals an imbalance in characteristics between the randomization arms, we will evaluate these characteristics as potential confounders in a sub-analysis secondary to the ITT as described in the mortality time to event analyses. Potential baseline confounders will be added stepwise in the linear regression model with randomization arms and maintained in the model if inclusion in the model changes the effect estimates (difference in means) by more than 10%.

In a per-protocol analysis, also secondary to the ITT analysis, a linear regression model will be fit as described above among the subset of children with documented completion of the full course of treatment (direct observation of 3 daily doses).

10.2 Secondary Objectives

1. *To compare changes in markers of acute malnutrition (Δ MUAC and Δ WLZ and Δ weight) in the 90 days following an episode of high risk diarrhoea without dysentery among children 2 to 23 months of age living in low resource settings who are randomized to receive a 3-day course of azithromycin or placebo.*

Linear regression (and associated z-test) will be used to compare mean Δ MUAC and Δ WLZ and weight across the treatment groups among surviving children.

2. *To evaluate (as determined by Verbal and Social Autopsy – VASA) cause-specific mortality rates across randomization arms in the 180 days following an episode of high risk diarrhoea without dysentery among children 2 to 23 months of age living in low resource settings who are randomized to receive a 3-day course of azithromycin or placebo.*

We will conduct Cox regression and K-M survival analyses (as described for aim 1) for time to cause-specific mortality (diarrhoea, pneumonia, malnutrition, other) as separate endpoints to understand intervention effects on specific causes of death.

3. *To compare the proportion of children hospitalized in the 90 days following enrolment for an episode of high risk diarrhoea without dysentery among children 2 to 23 months of age living in low resource settings who are randomized to receive a 3-day course of azithromycin or placebo.*

4. *To compare the proportion of children hospitalized or dying in the 90 days following enrolment for an episode of high risk diarrhoea without dysentery among children 2 to 23 months of age living in low resource settings who are randomized to receive a 3-day course of azithromycin or placebo.*

5. *To compare the proportion of children hospitalized or dying in the initial 10 days following enrolment for an episode of high risk diarrhoea without dysentery among children 2 to 23 months of age living in low resource settings who are randomized to receive a 3-day course of azithromycin or placebo.*

6. *To compare the presence of strains of *E. coli* resistant to selected antibiotics at enrolment between children in the different treatment arms entering the trial over time. Since children entering later into the trial are coming from the same communities, they can serve as a comparator group indicative of the community level of resistance.*

Prevalence of resistance to selected antibiotics and (with Wilson binomial 95% confidence intervals) will be calculated on all samples collected in Year 1 of the study, in Year 2 of the study and Year 3 of the study and compared using a chi-square test to determine the secular trend of evolution of antibiotic resistance at each site.

7. *To compare the presence of strains of *E. coli*, isolated from stools, and *S. pneumococcus*, isolated from nasopharyngeal swab, resistant to macrolide, β -lactamase and quinolone at DAY 90 and DAY 180 in a randomly selected sub-sample of children enrolled in the study and other children under age 5 years living in the same household.*

Prevalence of antibiotic resistance as a function of treatment group and time will be modelled using generalized estimating equations (GEE), with a Poisson link and exchangeable correlation structure for each antibiotic and each isolate, to account for repeated measurements within individuals. The GEE model will include three time-points (baseline, DAY 90 and DAY 180) for antibiotic resistance data from *E. coli* isolates and two time-points (DAY 90 and DAY 180 for *S. pneumoniae* isolates). Pairwise comparisons by treatment groups (azithromycin vs. placebo) at DAY 90 and DAY 180 and between baseline and DAY 180 (among the *E. coli* isolates) will be conducted using Wald tests. A Wald test will also be used to test the hypothesis

that the magnitude of change in prevalence, between treatment groups, differs at 90 days and 180 days (effect modification by time). Because multiple hypothesis tests will be performed (4 Wald tests per each of 8 antibiotics per each of 2 isolates types =56 tests) we will report p-values adjusted for multiple comparisons using a Bonferroni correction or a similar method.

For the siblings and close contacts, the same analytical methods will be used. However, no *E. coli* data from baseline will be collected therefore the *E. coli* GEE antibiotic resistance models will contain only two time points (DAY 90 and DAY 180).

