6.5 Collection and processing of biological specimens

A fecal sample will be collected from all children at enrolment. This sample will be aliquoted and stored at -80°C without further processing, to facilitate later molecular identification and analysis of enteric pathogens and their antimicrobial resistance genes.

A subset of up to 1600 to 1800 ABCD participants (approx. 15%) will be enrolled in a more detailed AMR sub-study. Random assignment into the AMR sub-study will be determined by the WHO Central Coordinating Office as part of the intervention randomization code, stratified by site and intervention arm. Children enrolled in the AMR sub-study will have a stool sample collected and processed at baseline, and a stool sample and a naso-pharyngeal swab collected

and processed for culture and resistance testing at DAY 90 and at DAY 180 after enrolment. In addition, a stool sample and a naso-pharyngeal swab will also be collected from a sibling or other close household contact (child contact) of the enrolled child (index-child) at DAY 90 and DAY 180.

The stool samples are primarily collected from whole stool passed by the study participant into a diaper or a container. If, however, the sample is taken at the study clinic (always on enrolment visit, sometimes on subsequent visits), and the child has not passed stool within 2-4 hours of the start of the clinic visit, and the primary caregiver gives a permission to the procedure, the stool sample may be taken with 2 cotton swabs, quickly inserted into the participant's rectum by a research nurse or physician.

Although it is determined at study enrolment whether the index child will participate in the AMR sub-study, no samples will be collected from the siblings or close household contacts before the 90 and 180-day time points. Eligible contacts are the participant's mother or children aged less than 60 months, who have slept in the same household as the enrolled child for 5 of the last 7-nights, and who share the same primary caregiver as the index child. If there are multiple contacts in the household who meet the eligibility criteria, then the preference for inclusion in the "contact study" will be given to the child closest in age and living in the same quarter as the index child. The contact will be the same child at DAY 90 and 180 so as to maintain the ability to evaluate within-individual change in resistance.

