The minimum isolate number required per treatment group was calculated assuming an alpha of 0.05 for two-way antibiotic resistance prevalence comparisons between randomization arms. We assumed a 15-20% prevalence of azithromycin resistance in the placebo arm at DAY 90, a slightly more conservative estimate than azithromycin-resistance estimates among *Shigella* isolates in Mirpur Bangladesh (22%) and in *E.coli* isolates in the Kongwa District of Tanzania (19%). We assumed that the increase in AMR would be about 2-fold at 90 days post enrolment. This is based on studies comparing azithromycin resistance in *S. pneumoniae* and *E. coli* between communities with and without community-wide azithromycin distribution which found resistance prevalence in the azithromycin-treated communities to be at least two-times

higher at 3 (30% vs. 10%) and 6 (23% vs. 12%) months after the antibiotic administration compared to untreated communities.

To achieve 90% power to detect a two-times higher prevalence in the azithromycin-treated arms, compared to 20% prevalence in the comparison group, we will need 119 *E. coli* and 119 *S. pneumoniae* isolates per treatment arm. We set this as the minimum number of children and siblings or close household contacts, from whom specific bacterial colonies would be available at the last data collection point on day 180. Accounting for losses at various points of study (as indicated in Table 2 below), a total of 345 children per arm (or 690 in total) would need to be recruited from both study regions (Asia and Africa). Given all the uncertainties in our assumptions and for logistical ease, we agreed to collect up from 1600 to 1800 study subjects allowing each site to collect isolates from approximately 250 children to this sub-study. For the four sites in Africa, this translates to approximately 1000 children enrolled in the AMR study and approximately 750 for the three sites in Asia

Table 2. Assumed losses of participants at the various stages of the AMR sub-study

Point in study	Cause of loss	% loss	Number of children / arm
Randomization to the AMR substudy (day 0)	Done at enrolment	0%	345
Available at day 90 visit	Death, other loss to follow-up between days 0 and 90	10%	311
1st sampling of study child (day 90)	Refusal of AMR sampling	20%	248
Recruitment of sibling or household contact (day 90)	No sibling or household contact available	20%	199

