4.6 Adjusting for baseline measure in change from baseline outcomes

Primary Objective 2 is change from baseline in length-for-age Z-score. Change from baseline outcomes will be adjusted for the baseline value in order to avoid the phenomenon of regression to the mean. In an analysis of covariance (ANCOVA) framework, this can be achieved by including baseline metric in the model. Identically, the same adjustment is achieved by including participant level covariates as random effects in a mixed effects model. This accounts for the clustering of length-for-age and weight-for-length across the two timepoints (enrolment and day 90) within each enrolled participant.

5 Hypotheses to be tested

Primary Objective 1 – 180 day mortality:

Null hypothesis: Among children 2-23 months of age with moderate to severe diarrhea, 180 day mortality is independent of treatment allocation to placebo or to a 3-day course of oral azithromycin.

Alternative hypothesis: Among children 2-23 months of age with moderate to severe diarrhea, 180 day mortality is not independent of exposure i.e. those allocated to receive a 3-day course of oral azithromycin compared to those allocated to receive oral placebo..

Primary Objective 2 – Change in Length-for-age z-score:

Null hypothesis: Among children 2-23 months of age with moderate to severe diarrhea, the mean change from baseline in length-for-age z-score (ΔLAZ) over the 90 day follow-up period is independent of treatment allocation to placebo or to a 3-day course of oral azithromycin.

Alternative hypothesis: Among children 2-23 months of age with moderate to severe diarrhea, the mean change from baseline in ΔLAZ over the 90 day follow-up period is not independent of exposure i.e. among those treated with a 3-day course of oral azithromycin than those treated with a placebo preparation.

Secondary objective 1 – Hospitalization by day 90

Null hypothesis: Among children 2 to 23 months of age with moderate to severe diarrhea, the proportion of children hospitalized by day 90 after enrolment, is independent of treatment allocation to placebo or to a 3-day course of oral azithromycin.

Alternative hypothesis: Among children 2 to 23 months of age with moderate to severe diarrhea, the proportion of children hospitalized by day 90 after enrolment, is not equal in the placebo arm and the arm receiving 3-day course of oral azithromycin.

Secondary objective 2 – Hospitalization or death by day 90

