9.5.2 Analysis

Four non-superiority hypothesis tests (2 samples and 2 timepoints) will be conducted to test whether the difference in prevalence of resistance at day 90 and day 180 in children assigned

to the azithromycin (R_{AZM}) and placebo ($R_{placebo}$) group exceeds a margin of 10% (one sided test).

E. coli Day 90

H_0 : $R_{AZM} - R_{placebo} > 10\%$
 H_1 : $R_{AZM} - R_{placebo} \leq 10\%$

E. coli Day 180

H_0 : $R_{AZM} - R_{placebo} > 10\%$
 H_1 : $R_{AZM} - R_{placebo} \leq 10\%$

S. pneumoniae Day 90

H_0 : $R_{AZM} - R_{placebo} > 10\%$
 H_1 : $R_{AZM} - R_{placebo} \leq 10\%$

S. pneumoniae Day 180

H_0 : $R_{AZM} - R_{placebo} > 10\%$
 H_1 : $R_{AZM} - R_{placebo} \leq 10\%$

Justification for the NI margin of 10%: this margin has been chosen based on clinical acceptability among infectious disease experts. Also, consultation with investigators in other trials of azithromycin accept a 10% (absolute difference) NI margin as reasonable. The non-inferiority hypothesis will be tested using the continuity corrected χ^2 test as suggested by Dunnett and Gent, Biometrics 1977.

In primary analysis, the prevalence denominator will be all children enrolled in the AMR sub-study whose stool was submitted for antimicrobial sensitivity testing (irrespective of whether the bacteria was isolated). Those children who were enrolled in the AMR study, who provided a sample, but whose sample could not be subject to an antibiotic sensitivity test because of external circumstances (COVID-19 related lockdowns of the lab), will be excluded from the denominator. At sites, that have experienced a lockdown, random distribution of selection of specimens for testing will be difficult to confirm, though examination for systematic bias (eg by date range) will be undertaken. If bias is suggested in sites that have not completed testing, these sites will be excluded from hypothesis testing. But other remaining sites will be included in non-inferiority test as outlined above.

In secondary analysis, the prevalence denominator will be defined as those children in whom the respective bacteria was isolated and tested (i.e. azithromycin resistance in *E. coli* as a proportion of *E. coli* isolates, and likewise for *S. pneumoniae*). Sites that have not completed testing as outlined above, will be dealt with as outlined above.

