9.5.3. Exploratory analyses

For both the primary and secondary analyses, estimates of AMR prevalence will be adjusted for site and other potentially confounding covariates (including those listed in Section 4.5, and data on recent antibiotic use). Resistance analyses will be reported separately for Asia and African sites.

Change in resistance over time within individual participating children will be estimated using mixed effects models or by including baseline MIC in the model. If MICs will be reported as ordered categories then ordinal mixed effects models will be used. If reported categorically as Resistant/Sensitive then binomial mixed effects models will be used.

We will also describe the resistance prevalence in *E.coli* at baseline for both trial arms.

If azithromycin resistance is detected among participants' samples tested, then a separate exploratory analysis on resistance to one or more β -lactam antibiotics will be done.

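### The participant E. coli non-inferiority tests leave out the pre-dose resistance result and the country term; the loss is precision only, and small unless baseline and follow-up resistance are well correlated

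*Protocol*

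**What the plan says.** Protocol 6.5: "Children enrolled in the AMR sub-study will have a stool sample collected and processed at baseline". The site plans that give an order, such as Kenya's (13.3), collect the stool before the first dose.

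Protocol 10.2, objective 7, plans a GEE for resistance prevalence: "The GEE model will include three time-points (baseline, DAY 90 and DAY 180) for antibiotic resistance data". This three-visit model is for E. coli; S. pneumoniae has the two follow-up visits only. The arms are then compared at day 90 and at day 180. No baseline covariate is named, and nothing says whether the two arms share a mean at enrolment.

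SAP 9.5.2 takes a different route: "Four non-superiority hypothesis tests (2 samples and 2 timepoints) will be conducted to test whether the difference in prevalence of resistance at day 90". The same test is repeated at the later visit, and the margin is 10 points each time. The named method is the Dunnett-Gent continuity-corrected chi-square, with no covariates. Baseline E. coli resistance is otherwise described only (SAP objective 7 and 9.5.3). The one model that may use it is exploratory and concerns change within a child: mixed effects "or by including baseline MIC in the model".

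SAP 4.3 says that every primary and secondary analysis will carry fixed effects for country, because randomisation was stratified by country. In the resistance sections, adjustment for site appears only under the exploratory headings.

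**The concern.** A pre-dose value of the same outcome in the same child is usually a useful covariate. Here it is already planned, sampled and cultured, so leaving it out of the confirmatory test saves no data collection. The two E. coli tests bear on whether azithromycin can be said to raise resistance by less than 10 points, and a wider interval makes that harder to show. The missing country term is a separate gap against the SAP's own rule, in the same few lines of text.

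The protocol's GEE does not settle the matter. If it is fitted with unconstrained arm-by-time terms, the day-90 and day-180 contrasts are the crude ones, and the baseline rows contribute nothing to them.

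**Working it through.** **The plan's own sizing.** Protocol 10.3 works "assuming an alpha of 0.05 for two-way antibiotic resistance prevalence comparisons between randomization arms" and states its target: "To achieve 90% power to detect a two-times higher prevalence in the azithromycin-treated arms, compared to 20% prevalence in the comparison group". Without continuity correction, two-sided:

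n = [1.960 × √(2 × 0.3 × 0.7) + 1.2816 × √(0.2 × 0.8 + 0.4 × 0.6)]² / 0.2² = (1.2702 + 0.8105)² / 0.04 = 108.2, so 109.

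With continuity correction: (108.2/4) × [1 + √(1 + 4/(108.2 × 0.2))]² = 118.0, so 119. The protocol's 119 per arm is reproduced. The Table 2 losses also agree: 345 × 0.9 × 0.8 × 0.8 × 0.67 × 0.9 = 119.8. This sizing is for a doubling of resistance, not for the SAP's 10-point margin.

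**Inputs for the SAP test.**
- Children: about 1000 in Africa and 750 in Asia (protocol 10.3). After 10% loss and 20% refusal: 1750/2 × 0.9 × 0.8 = 630 tested stools per arm at day 90.
- Placebo prevalence: 20% (upper end of the protocol's 15-20%).
- Margin: 10 points, one-sided (SAP 9.5.2). The SAP does not state the level; 0.025 is assumed.
- True excess: 3 points, assumed.
- r, the correlation between enrolment and follow-up status: not in the documents; 0.1 to 0.4 is shown.

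**Formula.** Adjustment multiplies the variance by (1 − r²). Unpooled normal approximation, without the Dunnett-Gent correction:

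SE = √[(0.20 × 0.80 + 0.23 × 0.77)/630] × √(1 − r²) = 0.02313 × √(1 − r²)

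Power = Φ[(0.10 − 0.03)/SE − 1.96]

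| r | Variance reduction | SE multiplier | Power |
|---|---|---|---|
| 0 (crude) | – | 1.000 | 85.7% |
| 0.1 | 1% | 0.995 | 86.0% |
| 0.2 | 4% | 0.980 | 87.0% |
| 0.3 | 9% | 0.954 | 88.7% |
| 0.4 | 16% | 0.917 | 91.0% |

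With no true excess, SE = √(0.32/630) = 0.02254 and crude power is Φ(0.10/0.02254 − 1.96) = 99.3%.

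At day 180 a further 10% loss leaves 630 × 0.9 = 567 per arm. With the 3-point excess, SE = √(0.3371/567) = 0.02438 and crude power is Φ(0.07/0.02438 − 1.96) = 82%. At r = 0.4 it is Φ[0.07/(0.02438 × 0.917) − 1.96] = 88%.

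**Simulation.** With 119 per arm, the ratio of adjusted to crude SD was 0.999, 0.982, 0.958 and 0.920 at r = 0.1 to 0.4, close to the multipliers above. A plain change score did worse than no adjustment at these correlations (SD ratio 1.19 at r = 0.3).

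**The GEE.** With 133 per arm and complete data, the day-90 log risk ratio from an unconstrained arm-by-time model equalled the crude value to about 1e-15. A common enrolment mean cut its SD from 0.269 to 0.261 at r = 0.3, and from 0.259 to 0.228 at r = 0.5.

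The gain from the country term cannot be computed, because the documents give no resistance prevalence by country.

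**The case against.** The strongest objection is that the benefit rests on a number nobody has. Nothing in the documents supports r of 0.3-0.4 over 90 to 180 days. Protocol section 11 says macrolide resistance falls quickly once treatment stops; this concerns mass dosing, so it is indirect, but it does not suggest strong persistence. At r = 0.1-0.2 the gain is negligible: the 95% half-width at 630 per arm moves from 4.53 to 4.51 or 4.44 points. This stands.

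The scenario can also be questioned. The 3-point excess is an assumption. The 20% refers to isolates, while the SAP's primary denominator is all tested stools. With E. coli grown from 76-91% of stools, 20% of isolates is about 15-18% of stools. At 15%, crude power is Φ{0.07/√[(0.15 × 0.85 + 0.18 × 0.82)/630] − 1.96} = 91.8%. This stands too, and lowers the stakes.

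Some handling already exists. SAP 4.4 puts apparent baseline imbalances into sensitivity analyses for all primary and secondary outcomes, and 9.5.3 allows exploratory adjustment with an open list of covariates. Neither reaches the confirmatory test.

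Five stronger readings might be inferred, and the documents do not support them:
- That chance baseline imbalance is a further harm. At 20% prevalence the SE of the baseline difference is √(0.32/630) = 2.3 points, but it reaches the follow-up contrast only in proportion to r (about 0.7 points at r = 0.3). It is the same variance, already counted.
- That SAP 4.6 is breached. Its rule is "Change from baseline outcomes will be adjusted for the baseline value", and the resistance outcome is prevalence at a visit, not change.
- That a weak regional test is at stake. SAP 9.5.2 plans no test by region; regional results are only reported, under the exploratory heading.
- That the protocol's GEE certainly wastes the baseline. Its parameterisation is not stated.
- That every AMR child has a baseline MIC. Some stools grow no E. coli, and not every enrolment stool need have been tested.

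**Conclusion.** The point holds for E. coli in enrolled children. The SAP 9.5.2 tests ignore a pre-dose result that the sub-study already collects, and they omit the country term that SAP 4.3 requires. There is no bias: under randomisation the crude test is valid, and what is given up is precision. On planned numbers and the stated assumptions, that is between almost nothing (r = 0.1-0.2) and about 5 points of power (r = 0.4, from 86% to 91%), and less if the true excess is near zero. The number of children enrolled when recruitment stopped, and the number of specimens tested after laboratory lockdowns, are not given. If they fall short of plan, crude power is lower than shown. The departure from SAP 4.3 does not depend on r.

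**What to change.** In SAP 9.5.2, for the two participant E. coli tests:
- Estimate the azithromycin-minus-placebo risk difference from a model with arm, country and enrolment E. coli status in four categories: resistant, not resistant, none isolated, not tested.
- Standardise it to a marginal difference and compare its upper confidence limit with the unchanged 10-point margin. State the one-sided level.
- Keep the Dunnett-Gent test as a sensitivity analysis. Do not substitute a change score.

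If the protocol 10.2 GEE is still to be used, specify a common enrolment mean for the two arms.

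S. pneumoniae and contacts have no baseline sample, so the baseline adjustment does not apply to them. Their tests also lack a country term, and the SAP should say how 4.3 applies there.

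The cost is a few lines of SAP text and a somewhat more complex analysis in place of a simple named test. No new data are needed, and enrolment status is pre-dose, so a not-tested category is acceptable. The choice should be fixed before the intervention code is broken.
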